### 3.5.3 Participant eligibility and recruitment

To be enrolled into this study, the participants will have to match the following criteria: (a) currently receiving treatment at the selected OAT site (this also implies that the patient is (i) 18 years of age or older, (ii) meets ICD-10 criteria for opioid dependence, (iii) residing within the study catchment area); (b) not planning to move to another region in the upcoming 6 months; (c) ability to provide informed consent; (d) having a positive HCV antibody test documented in the medical chart; (e) no history of HCV treatment in the past by self-report; (f) not being pregnant and not planning pregnancy in the next 3 months; (g) absence of active TB; (h) interest in study participation.

Participants will be recruited using the following systematic random sampling procedure, adapted from our previous studies. At the first step, the OAT site staff will prepare a de-personalized list of all patients with their patient IDs (without names to maintain confidentiality), OAT admission dates, dates of most recent HCV screening test documented in their medical chart, and test result. At the second step, the study data manager will filter out patients without positive HCV test result, and apply a random number generator to sort potentially eligible patients in random order, which will form a Screening Log. At the third step, the clinical staff responsible for recruitment will contact the patients in the order of appearance in the Screening Log for eligibility screening. During the eligibility screening, the clinical staff will assess patients' cognitive ability, ask patients about their plans to stay in the same city for the next 6 months, and about their prior history of HCV treatment. The results of the screening procedures will be documented in the Screening Log. Additionally, during eligibility screening, patients are screened for TB symptoms (night sweats,

cough for more than 2 weeks, unusual weight loss, fever). Patients who present any of these symptoms are referred for TB diagnosis. In case of TB diagnosis, patients are referred for TB treatment and HCV treatment is postponed. Those who are Patients meeting all criteria will be referred to the interviewer to finish the remaining enrollment procedures, which include informed consent, completion of locator information. Reasons for declining study participation will be documented.

Eligibility screening and recruitment will stop once the target sample size is reached. If the required number of participants is not recruited when the end of the patient list is reached, the sites will be instructed to encourage patients without a documented HCV test result to undergo screening. Majority of the OAT clinics are able to provide anti-HCV testing on-site or by referral to harm reduction programs, which routinely provide this testing to PWID at no charge. Patients who test positive will be added to the Screening Log and will be screened for other eligibility criteria.

Diagnosis confirmation will be done using HCV RNA PCR test (qualitative or quantitative). Each site will decide on the most convenient option for test provision – optimally with blood sample collection on-site. In case diagnosis is not confirmed, the patients will be excluded from the study. Baseline survey will be administered after diagnosis confirmation, for patients with a positive test.

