#### (1) diagnosis

Majority of the OAT programs in Ukraine already have reasonably high rates of HCV screening (~80% according to our preliminary data), therefore we will enroll patients who have a documented anti-HCV antibody test result. Patients without a documented test result will be referred to receive HCV screening on-site or at a local harm reduction program where it is provided at no cost.

We will evaluate and compare the HCV treatment cascade outcomes starting from HCV diagnosis (HCV RNA test). Where available, a qualitative HCV RNA assay with a lower limit of detection of  $\leq 1,000$  IU/ml will be used to minimize the costs.

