### 3.2 Provision of DAA medications and laboratory tests

To enable on-site medication prescription and dispensing, we will work with the MoH through an established working group to re-route the required number of treatment courses procured by the MoH or regional programs to the OAT clinics.

Due to the centralized procurement (see Rationale), all regions have approximately same ratio of available formulations (with SOF+DAC comprising about 65% in the 2019 procurement). We will ensure that OAT clinics have at least one pan-genotypic regimen available (SOF+DAC or SOF/VEL). **Given the implementation science premise of this proposal, we will not control which regimens are prescribed by physicians.** Available pangenotypic DAA regimens are expected to have comparable effectiveness in our study population [16, 23]. Given that, and assuming even prevalence of genotypes and complicating conditions (e.g. cirrhosis) across the regions, we may safely assume that overall treatment effectiveness will not differ a priori, and the observed differences will result from the study interventions.

Medications will be provided to patients at no cost.

Currently, the diagnostic tests for HCV are provided at a wide range of public and private clinics and laboratories, however these assessments have to be paid for by patients. The average total cost for pre-treatment assessment is about \$100, including the complete blood count, metabolic panel, hepatic function panel, fibrosis staging, INR, but not including elastography. Given the implementation science nature of the proposed research, focusing on real-life outcomes, the costs of laboratory testing will NOT be covered by the project.

For those participants who complete HCV RNA PCR to confirm SVR, HCV RNA PCR for re-infection assessment (12 month after treatment completion) will be recommended. Cost of re-infection assessment will be reimbursed by the project.

### 3.3 Research methods for Aim 1

1) To develop SHIM and demonstrate its feasibility. We will finalize SHIM, train the clinicians and conduct a pilot-test in 10 OAT patients with HCV infection.

We will establish a technical working group on viral hepatitis elimination to finalize SHIM and oversee the study progress. The group will review the latest consensus documents [24], guidelines

(WHO, EASL, AASLD), and the National Standard [22] and produce a localized manual for simplified HCV integrated management model in non-specialty health care institutions.

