### 3.5.5 Secondary Endpoints

Secondary outcomes will include the interim cascade steps:

- S1a. Testing for HCV RNA;
- S1b. Assessment of fibrosis staging;
- S1c. Completion of DAA treatment (receiving the last prescribed medication supply);
- S1d. Testing for HCV RNA at 12 weeks after treatment completion;

Factors that affect treatment effectiveness:

- S2a. DAA treatment motivation (summary score measured by the investigator-developed questionnaire at baseline);
- S2b. DAA treatment adherence (defined as percentage of doses taken using two measures: visual analog scale administered at treatment completion, and pill counts at each dispensing visit);
- S2c. Treatment satisfaction (measured by investigator-developed questionnaire at treatment completion);

Treatment outcomes:

- S3a. Quality of Life (measured by SF-12 questionnaires at all four interviews);
- S3b. Re-infection (measured at 12 months after treatment completion among those achieving SVR).

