### 3.5.6 Data collection

Given the primary and secondary outcomes of interest, data collection for Aim 1 will include three main sources: clinical chart review data and quantitative survey of patients.

**De-identified medical chart review** data extracted by authorized clinic staff will inform outcomes P1-P3, S1a-d and S3b. We will use the electronic Simple Treatment Monitoring Application (STMA)

developed and used in our previous [35] and ongoing projects to collect detailed data on all relevant assessments and treatments, including HCV diagnostic tests, pre-treatment assessments, DAA treatment prescription, on-treatment and post-treatment monitoring, OAT admission and discharge, OAT medication prescription. The database will also collect information on important clinical covariates, including HIV, TB and HBV co-infection, mental health screening and its results, prescription of ART and other medications and side effects. STMA data will be collected on a monthly basis from all sites.

It is expected that physicians at the SHIM sites will comprehensively manage HCV care, and the medical charts and STMA will contain all up-to-date diagnostics and treatment information. However, all SOC sites' patients and possibly some SHIM patients will receive HCV services elsewhere, and their HCV-related clinical data will not be available at the OAT clinic. To ensure completeness of the key outcome data for all participants, we will use an external clinical data verification procedure, similar to one used in our ongoing IMPACT project. In order to avoid intervention contamination, this procedure is conducted by research staff, and not by OAT clinic personnel. At the end of each quarterly clinical data collection cycle, the data manager will generate the HCV treatment cascade report in STMA. For each patient who will not have information about any of the three primary clinical endpoints (HCV diagnosis, treatment initiation, post-treatment HCV RNA PCR) in the report, the interviewers will conduct a brief follow-up by phone. If the patient will report receiving this service, the interviewer will ask about when and where the service was received. At the second stage, the interviewers will contact the respective healthcare facilities to verify the receipt of the services and results (for assessments). This procedure will be enabled by a separate third-party disclosure agreement signed by the patient.

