For the secondary outcomes S2b-c, we will collect data using a **paper-based adherence form** administered by clinical personnel during patient visits at treatment initiation, medication pick-up at 4 and 8 weeks, and treatment completion at 12 weeks after initiation. The baseline form will assess self-efficacy and anticipated barriers to treatment adherence for the whole treatment period. The follow-up forms will assess treatment satisfaction, past 30-day and 7-day adherence using visual analog scale [36], side effects, reasons for non-adherence, and reasons for treatment discontinuation (if occurred). At treatment completion, the form will additionally assess the readiness and anticipated barriers to SVR check at 12 weeks after.

For the secondary outcomes S2a and S3a and relevant co-variables, we will collect data using a **patient survey**. The survey will be conducted for the pilot patients and all 3 arms of the main phase at baseline, treatment completion (or 12 weeks after initiation if not completed or 16 weeks after the baseline if not started) and 12 weeks after treatment completion (or 24 weeks after treatment initiation if not completed, or 28 weeks after the baseline if not initiated treatment).

The baseline survey will be administered after confirmation of the diagnosis using HCV RNA test. Patients who will test negative for HCV RNA will be excluded from the following study procedures.

All patient surveys will be collected by an independent interviewer, using study ID via UIPHP REDCap server with clerical checking and patient safeguards described in detail in the human subjects section.

The surveys will include demographics, geospatial assessment, depression (PHQ-9), substance use, alcohol use disorders (AUDIT-C), HIV comorbidity and treatment history, Chronic Liver Disease Questionnaire-Hepatitis C Version (CLDQ-HCV) [37], trust in physician scale [38, 39], HIV risk behaviors, family and social support [40], drug use and mental illness stigma [41], and socio-demographic information.

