Aim 3's analysis will involve three distinct strategies. First, we will examine the time difference in HCV cascade elements (% diagnosed, % treated, % achieving SVR), with sub-analyses for geographic area and OAT dropout +/- ECHO vs SOC setting. To do this, we will use a generalized mixed linear model (with a logit link), where group will vary by either study arm or by geographical area. Our dependent variables will include: 1) a binary indicator for whether an individual patient achieved the desired HCV diagnosis/treatment coverage cut-off (e.g. diagnosis coverage >80%), as previously used to measure comprehensive and holistic integrated primary care for PWID receiving buprenorphine [42]. The same approach will then be used for secondary individual outcomes (treatment motivation and adherence, treatment satisfaction, quality of life), which we have done previously when integrating addiction treatment into specialty services in the US [43] and Ukraine [12]. 2) treating the primary and secondary indicators as a continuous variables. Any changes in national guidelines that might influence HCV treatment availability would not be scored until after at least 1 year after publication in order to allow for uptake changes by clinicians. Our covariates will include time trends, client-level variables including demographic characteristics, fibrosis stage, treatment motivation and adherence, addiction severity and mental health measures, as well as organizational and provider level measures (from Aim 2).

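### The baseline survey waits for a positive HCV RNA result, itself a compared outcome, so enrolled patients who are never tested have no baseline survey and no date for their follow-up surveys

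*Combined protocol and SAP*

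**What the plan says.** The rule appears twice. Section 3.5.3 has "Baseline survey will be administered after diagnosis confirmation, for patients with a positive test", and Section 3.5.6 repeats it: "The baseline survey will be administered after confirmation of the diagnosis using HCV RNA test".

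The same test is an outcome. Section 3.5.5 lists "S1a. Testing for HCV RNA" among the interim cascade steps. Under SHIM step (1) in Section 3.1.2 the plan states: "We will evaluate and compare the HCV treatment cascade outcomes starting from HCV diagnosis (HCV RNA test". Section 3.5.6 counts diagnosis among the "three primary clinical endpoints (HCV diagnosis, treatment initiation, post-treatment HCV RNA PCR" for which missing records are chased by telephone.

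For patients who never start treatment, Section 3.5.6 sets the second survey at "16 weeks after the baseline if not started" and the third at 28 weeks on the same basis.

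Section 3.5.5 defines S2a (treatment motivation) from the baseline questionnaire alone and takes S3a (SF-12) from the interviews. The broader model in Section 3.5.8 includes among its covariates "fibrosis stage, treatment motivation and adherence, addiction severity and mental health measures".

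**The concern.** A baseline measure should be available for everyone enrolled and should not depend on what happens to them afterwards. Here it is collected only from patients who have already obtained an RNA test with a positive result. Clinics are randomised and patients consent before that point, so having a baseline survey is conditional on a post-randomisation event that the trial sets out to compare.

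At stake are S2a, the starting value of S3a, and the survey covariates. If the share tested differs between arms, the surveyed groups are no longer the groups that were enrolled, and comparisons of S2a and S3a lose the protection of randomisation. The timing rule adds a second gap. A patient who is never tested never starts treatment within the plan's pathway, so the only survey dates that apply are counted from a baseline that does not exist.

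**Working it through.** The point is one of design logic, and the plan states no figure to reproduce. The relevant texts, side by side:

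1. **Entry.** Section 3.5.3 requires a documented positive antibody test, with consent and locator details completed by the interviewer. No RNA result is among the listed criteria.
2. **Untested patients remain.** Under Section 3.5.7, not completing the clinical work-up is not a reason for withdrawal. The cascade denominator in Section 3.5.8 is antibody-positive enrolled patients. The telephone procedure in Section 3.5.6 covers patients with no diagnosis on record, so such patients are foreseen.
3. **Survey trigger.** A positive RNA result (Sections 3.5.3 and 3.5.6).
4. **Follow-up dates.** Surveys 2 and 3 of non-starters run from the baseline (Section 3.5.6). No substitute such as the consent date is given.

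Together, an enrolled patient who is never tested counts in the denominator, has no baseline survey, and has no due date for the later ones.

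**What is still observed.** P1 to P3 come from chart review with external verification (Section 3.5.6), which also records co-infections, prescriptions and mental health screening. The primary model adjusts for region, age and gender (Section 3.5.8).

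**Possible size.** The documents give no testing rates, so the shares below are assumptions. RNA-negative patients are ignored: the 160 per arm are treated as patients not excluded for a negative result. With untested shares u:

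number without a baseline survey = 160 × u(SOC) + 2 × 160 × u(SHIM)

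Example: 160 × 0.20 + 320 × 0.05 = 32 + 16 = 48, and 48/480 = 10.0%.

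| SOC untested | SOC patients with survey | Total missing if 5% untested in each SHIM arm (152 surveyed per arm) | Total missing if 10% untested in each SHIM arm (144 surveyed per arm) |
|---|---|---|---|
| 10% | 144 | 32 (6.7%) | 48 (10.0%) |
| 20% | 128 | 48 (10.0%) | 64 (13.3%) |
| 30% | 112 | 64 (13.3%) | 80 (16.7%) |
| 40% | 96 | 80 (16.7%) | 96 (20.0%) |

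Section 3.5.8 expects to collect more than 90% of survey data at 24 weeks. If that is counted over all 480 enrolled, fewer than 48 may be missing. The limit is reached when 160 × u(SOC) + 320 × u(SHIM) = 48, that is, when u(SOC) + 2 × u(SHIM) = 0.30. Examples are 20% in SOC with 5% in each SHIM arm, or 10% in every arm, in both cases before any ordinary loss to follow-up.

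**The case against.** **RNA confirmation may be an entry condition.** The sentence just before the survey rule in Section 3.5.3 excludes patients whose diagnosis is not confirmed, and the aims speak of HCV-infected patients. If that covers the never-tested, nobody without a baseline survey remains. The reading is possible, but S1a would then be 100% in every arm by construction, and it sits badly with Sections 3.5.7 and 3.5.8 and the telephone follow-up. Section 3.5.6 limits the exclusion to patients who test negative. The ambiguity stands and must be resolved.

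**The schedule table.** A reader might infer that the table in Section 3.5.6 contradicts the rule by placing the survey at enrolment. It does not: diagnosis confirmation and survey share that column, and no order between them is shown.

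**The primary comparison.** A reader might infer that the treatment-initiation contrast is distorted because untested patients drop out of the model. That would need a complete-case fit of the broader covariate model. The plan does not specify one; it names a likelihood-based mixed model under MAR, with multiple imputation as an example of a sensitivity method. This part of the objection stands. Those methods do not by themselves repair missingness defined by an outcome step, since untested patients contribute no survey data at all.

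**Imbalance between arms.** SOC patients are referred elsewhere, and hypothesis 1 predicts better uptake under SHIM. But "the costs of laboratory testing will NOT be covered by the project" applies in every arm, and each site chooses how RNA testing is provided. That the gap falls mainly on SOC is an inference, not a documented fact.

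**Design preference.** Asking hepatitis C-specific questions only of patients with confirmed infection is defensible. It has to be weighed against losing the baseline for untested patients.

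**Conclusion.** The point holds for the survey data. As written, enrolled patients who are never RNA-tested have no S2a, no baseline S3a, no survey covariates and no due dates for later surveys, so these measures are observed only in patients who passed a post-randomisation step. This rests on reading the exclusion in Section 3.5.3 as RNA-negative patients only, which most of the other text supports.

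The size is unknown. The assumed shares above give 6.7% to 20% of patients without a baseline survey, and those figures are illustrations only. The gap exists even with equal shares in all arms; unequal shares would add bias to between-arm comparisons of S2a and S3a.

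Two stronger conclusions are not supported. Untested patients are not without any baseline data, because chart data exist. And the primary analysis adjusted for region, age and gender is not directly affected, provided age and gender come from a source other than the survey. Demographics are listed among the survey items; Section 5.4 says age stays on the record, but no other source for gender is named.

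**What to change.** - Give the baseline survey at the consent visit, before RNA testing, to every enrolled patient in all three arms. Section 3.5.3 already has an interviewer meeting each patient then.
- Amend the survey rule in Sections 3.5.3 and 3.5.6, and show the order of consent, survey and RNA test in the schedule table.
- Time the 16- and 28-week surveys of untested or untreated patients from the consent date.
- Reconcile the exclusion sentence in Section 3.5.3 with Sections 3.5.5 to 3.5.8: only RNA-negative patients are excluded, and untested patients stay in.
- Name the source of age and gender for the primary model.

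The cost is protocol wording, a change in interviewer timing, some surveys in patients later found RNA-negative, and survey follow-up of untested patients. The change does not settle a separate matter in Section 3.5.8: fibrosis stage and adherence arise after baseline, and adherence exists only for treated patients, whenever the survey is given.

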### 3.5.4 Primary Endpoints

Primary outcomes are based on the HCV treatment cascade:

- P1. Completing pretreatment evaluation (completing all clinical and laboratory assessment prescribed by the physician according to the SHIM algorithm);
- P2. Initiating DAA treatment (taking the first dose of DAA medication prescribed by the physician);
- P3. Achieving SVR12 (having an undetectable HCV RNA PCR result at 12 weeks after treatment completion).

### 3.5.5 Secondary Endpoints

Secondary outcomes will include the interim cascade steps:

- S1a. Testing for HCV RNA;
- S1b. Assessment of fibrosis staging;
- S1c. Completion of DAA treatment (receiving the last prescribed medication supply);
- S1d. Testing for HCV RNA at 12 weeks after treatment completion;

Factors that affect treatment effectiveness:

- S2a. DAA treatment motivation (summary score measured by the investigator-developed questionnaire at baseline);
- S2b. DAA treatment adherence (defined as percentage of doses taken using two measures: visual analog scale administered at treatment completion, and pill counts at each dispensing visit);
- S2c. Treatment satisfaction (measured by investigator-developed questionnaire at treatment completion);

Treatment outcomes:

- S3a. Quality of Life (measured by SF-12 questionnaires at all four interviews);
- S3b. Re-infection (measured at 12 months after treatment completion among those achieving SVR).

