In addition, we have planned to test for a linear trend among the intervention levels for the proposed outcomes, testing that SHIM+ECHO > SHIM with No ECHO > SOC. We also plan to test the treatment effects using similar methods for OAT dropout strata separately. In addition to direct effects, mediation and moderation regression will be conducted as described by Donaldson. Testing will be conducted at a Bonferroni corrected type I error level of 0.025 to control for multiple testing. Secondary and process outcomes will similarly be tested. These measures and their subscales will be compared as pre/post and over time using one-way ANOVA/Duncan test, with general linear models to identify differences in treatment effect stratified by the geographic region (cluster). Mean scores will be normalized, with comparisons between the three groups, with the referent being SOC. To address multiple testing, we will use the Benjamini-Hochberg method of controlling the false discovery rate. We do not expect missing data to be a concern since most of the data on primary outcomes will be derived from clinical source documentation; for the survey data, we expect that we will collect more than 90% of the data at the 24-week time point. We will, however, explore all patterns of missing data and compare those with and without data to determine whether the data may be MAR or not MAR (i.e. eliminate the missing completely at random assumption). We will conduct sensitivity analyses using an appropriate missing data method, such as multiple imputation.

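### Treatment motivation (S2a) is defined at baseline only, after a positive RNA test, yet is analysed as a secondary outcome by arm, pre/post and over time; no repeat measurement is specified.

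*Combined protocol and SAP*

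**What the plan says.** Section 3.5.5 lists motivation among the secondary endpoints, under the sub-heading "Factors that affect treatment effectiveness": "S2a. DAA treatment motivation (summary score measured by the investigator-developed questionnaire at baseline". The Summary also names it as a secondary outcome. Timing in Section 3.5.5 is given item by item; quality of life, by contrast, is explicitly repeated: "S3a. Quality of Life (measured by SF-12 questionnaires at all four interviews".

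On when baseline falls, Section 3.5.3 says: "Baseline survey will be administered after diagnosis confirmation, for patients with a positive test". Section 3.5.6 repeats this, and patients who test RNA-negative leave the later procedures.

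Section 3.5.6 says that S2a and S3a data come from the patient survey, given at baseline, at treatment completion and 12 weeks after completion, with substitute times for patients who do not start or do not finish. Motivation appears neither in its list of survey content nor in the items it adds at baseline or after treatment.

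Section 3.5.8 gives motivation two roles. It is an outcome: "The same approach will then be used for secondary individual outcomes (treatment motivation and adherence, treatment satisfaction, quality of life". It is also an adjustment variable: "Our covariates will include time trends, client-level variables including demographic characteristics, fibrosis stage, treatment motivation and adherence". Of the secondary and process outcomes in general, the section then says "These measures and their subscales will be compared as pre/post and over time using one-way ANOVA/Duncan test", and "Mean scores will be normalized, with comparisons between the three groups, with the referent being SOC".

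**The concern.** An outcome that is to be compared before and after, and over time, needs at least two measurements. The endpoint definition gives one. What remains is a comparison of the arms at a survey called baseline, and that survey is neither clearly pre-intervention nor taken in everyone enrolled. Sites are randomised, and Section 3.1.2 starts the compared cascade at the RNA test, so part of the care under comparison comes before the survey. Patients who never have the test get no score.

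Two things are at stake. A difference between arms in S2a could be read as an effect of SHIM or ECHO when the design cannot tell it from differences in who was recruited or tested. And as a covariate, motivation is missing for exactly the patients who fall out at the first step of the cascade.

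**Working it through.** The plan gives no sample size, power or effect size for S2a, so there is no figure to reproduce. The check has three parts.

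**1. Timing, side by side.**

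| Place | What it implies for S2a |
|---|---|
| 3.5.5 | One measurement, at baseline |
| 3.5.3 and 3.5.6 | Baseline survey follows a positive RNA test |
| 3.5.6, data sources | S2a comes from a survey given 3 times |
| 3.5.6, survey content | Motivation not listed at any time |
| 3.5.8, secondary outcomes | Modelled by arm; general wording adds pre/post and over time |
| 3.5.8, covariates | Motivation is an adjustment variable |

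One measurement time is stated and no follow-up time is. S2a is one of five non-cascade secondary outcomes (S2a, S2b, S2c, S3a, S3b).

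**2. What can be estimated.** Take a model with arm (3 levels), time (3 levels) and arm-by-time terms. It has 1 + 2 + 2 + (2 × 2) = 9 parameters. The rank of the design matrix is the number of arm-by-time cells observed:

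- baseline only: 3 × 1 = 3 of 9. Three arm means; no time and no arm-by-time term.
- baseline plus one later survey: 3 × 2 = 6 of 9. One change per arm.
- all three surveys: 3 × 3 = 9 of 9. All terms.

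With S2a as defined, 9 − 3 = 6 parameters cannot be estimated, and these are the ones that a pre/post or over-time analysis needs.

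**3. What the remaining contrast can carry.** A score exists only after RNA testing, which is outcome S1a. The documents give no testing rates, so the following is an illustration under assumptions. Let motivation be standard normal, with correlation ρ to a latent normal tendency to be tested; let a proportion p be tested; let motivation be unrelated to RNA positivity; and let there be no true effect on motivation. Then

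mean motivation among those tested = ρ × φ(c)/p, with c = Φ⁻¹(1 − p).

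The factor φ(c)/p is 0.644 at p = 0.60, 0.350 at p = 0.80, 0.195 at p = 0.90 and 0.109 at p = 0.95. Assume 60–80% tested under SOC, 90–95% under SHIM, and ρ between 0.2 and 0.4:

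- smallest gap: 0.2 × (0.350 − 0.195) = 0.03 SD
- largest gap: 0.4 × (0.644 − 0.109) = 0.21 SD
- equal testing rates: 0

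Under these assumptions selection alone makes the SOC mean higher, so it could hide a benefit. Recruitment differences or knowledge of the arm could push either way.

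**The covariate role.** Section 3.5.8 sets the denominator of every cascade indicator as all enrolled antibody-positive patients. If its diagnosed outcome means the RNA test, as in Section 3.1.2, every patient with a motivation score has already been tested. A complete-case model of that step then contains no failures, and imputation has no untested patient with a score to learn from.

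**The case against.** The strongest reply is that Section 3.5.6 links S2a to a survey run three times, so the items may well be repeated. The endpoint list is not plainly the authority on timing either: it refers to four interviews for quality of life, while Section 3.5.6 schedules three surveys. This stands in part. A reader might infer that no second measurement exists; the documents support only that none is specified. Section 3.5.6 names the instrument, not a schedule for the motivation items.

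A reader might also infer that S2a cannot show any effect of SHIM or ECHO, and that an arm difference could come only from recruitment or knowledge of the arm. The documents do not support that. Sites are randomised and the RNA test comes before the survey, so an early difference could partly reflect the intervention. The problem is that it cannot be isolated.

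Third, the pre/post sentence is blanket wording and fits some other outcomes no better: S2c is defined at treatment completion only, and S3b at 12 months only. That is fair, and it makes this a loose plan more than a deliberate one. But motivation is named individually among the secondary outcomes to be modelled by arm, so the conflict does not rest on the blanket sentence alone.

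Fourth, the sub-heading and the covariate list already give S2a a predictor role. That supports the fix; it does not resolve the double use. Finally, the documents give no evidence that testing rates differ by arm: each site chooses how the RNA test is provided, and laboratory costs are not covered, with no exception by arm. The direction and size of the selection shown above are therefore assumptions.

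**Conclusion.** The point holds in a limited form. As Section 3.5.5 defines it, S2a supports no pre/post or over-time estimate: 3 of 9 parameters are identifiable, and no follow-up time is specified. The only available contrast is between arms at baseline among RNA-positive patients, and it mixes any early intervention effect with recruitment, knowledge of the arm and selection into testing. Sections 3.5.5 and 3.5.6 must be reconciled on whether the items are repeated; if they are repeated at all three surveys, the estimability problem disappears. These conclusions follow from the text and do not depend on the assumed testing rates. The 0.03 to 0.21 SD range only illustrates what selection could do. One secondary outcome and one covariate are affected; the primary endpoints and the sample size are not.

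**What to change.** **Preferred.** Remove S2a from the outcomes tested by arm in the Summary and in Sections 3.5.5 and 3.5.8. Keep it as a baseline predictor or moderator for the steps after the RNA test, stating that such analyses apply to RNA-positive patients. Do not use it as a covariate in any model of RNA testing or diagnosis. The cost is wording only.

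**Alternative, if an effect on motivation is wanted.** Add the same items to the existing follow-up surveys for all participants in all three arms, list them in the survey content of Section 3.5.6, and name in advance one time point and one contrast. The cost is a short addition to surveys already scheduled. The repeat should not be confined to patients who have not started treatment: starting is primary endpoint P2, so the arms would be compared on groups selected by a post-randomisation outcome.

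**Optional.** The questionnaire could move to the consent visit, where Section 3.5.3 already places an interviewer, so that every enrolled patient has a score. Against this, it adds time for patients later found RNA-negative and excluded, and motivation for DAA treatment asked before infection is confirmed may be a different construct.
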